#### 10.3.6 Follow-Up of Unresolved Events

All AEs should be followed until they are resolved or the investigator assesses them as chronic or stable or the subject’s participation in the trial ends.

In addition, all SAEs and those non-serious events assessed by the investigator as related to the study medication should continue to be followed even after the subject's participation in the trial is over. Such events should be followed until they resolve or until the investigator assesses them as "chronic" or "stable." Resolution of such events is to be documented on the appropriate CRF.

#### **10.3.7 Special Situations**

Certain safety events, called 'Special Situations', that occur in association with study medication(s) may require reporting. These Special Situations include, but are not limited to, the following:

- Overdose of the medicinal product
- Suspected abuse/misuse of the medicinal product
- Inadvertent or accidental exposure to the medicinal product
- Medication error involving the medicinal product (with or without subject/patient exposure to the sponsor's medicinal product, eg, name confusion)
- Drug-drug interaction

Special situations should be reported on the Special Situations CRF whether they result in an AE/SAE or not. Special situations with associated AE/SAE should also be reported on the corresponding AE/SAE forms, following applicable AE or SAE process.

#### **10.4 Exposure In Utero**

A pregnancy in a female subject must be confirmed by a positive serum  $\beta$  human chorionic gonadotropin ( $\beta$ -HCG) test.

The study medication should be immediately discontinued once the pregnancy of a female study participant has been confirmed.

If any study participant becomes or is found to be pregnant while receiving a study medication or within 30 days of discontinuing the study medication, the pregnancy must be recorded on the Pregnancy Reporting Form/Exposure In Utero Form within 24 hours of awareness of the pregnancy and sent to the CRO via email or fax (reference the site manual for contact information).

Pregnancy during this time frame of the female partner of a male subject should also be reported.

The Pregnancy Reporting Form/Exposure in Utero Form must be completed with all known information regarding the pregnancy at the time of reporting. Investigative site personnel will update the form with additional information regarding the pregnancy and the outcome of the pregnancy as it becomes available until the outcome of the pregnancy is reported.

The investigator will follow the subject (or female partner of a male subject) until completion of the pregnancy. If the outcome of the pregnancy meets the criteria for immediate classification as an SAE (ie, spontaneous abortion, stillbirth, neonatal death within 1 month of birth, or congenital anomaly [including that in an aborted fetus]), the investigator should follow the procedures for reporting an SAE within 24 hours of awareness. A pregnancy in and of itself is not considered an AE; however, unexpected complications are considered AEs.

Additional information about pregnancy outcomes follows:

- Note that “spontaneous abortion” includes miscarriage and missed abortion.
- Neonates should be followed through gestational age of 46 weeks,
- Follow-up information includes the course, duration, and the outcome of the pregnancy and the neonate’s health.
- All neonatal deaths that occur within 1 month of birth should be reported, without regard to causality, as SAEs. In addition, any infant death after 1 month that the investigator assesses as related or unrelated to the in utero exposure to the study medication should also be reported.
- In the case of a live birth, the “normality” of the newborn can be assessed at time of birth.
- The “normality” of an aborted fetus can be assessed by gross visual inspection unless there are pre-abortion laboratory findings suggestive of a congenital anomaly.

## 11 DATA ANALYSIS

An overview of the statistical approach to the primary endpoint and safety analyses are provided below. The details of the planned analysis of the primary endpoint as well as the planned analyses of secondary endpoints, PK, and safety will be documented in the statistical analysis plan (SAP).

### 11.1 Primary Endpoint – Mean Change in Hb from Pre-treatment to the End of the Primary Efficacy Period (Week 6)

The primary objective of this study is to evaluate the dose-response relationship between oral vadadustat once daily dosing for 6 weeks and change in Hb in Japanese subjects with anemia secondary to NDD-CKD, to define the starting dose for use in Phase 3 clinical studies in Japan.

The primary endpoint is the mean change in Hb from pre-treatment to the end of the primary efficacy period (Week 6). Pre-treatment Hb is defined as the average of 2 Hb values obtained prior to treatment based on the qualifying screening Hb value and the Hb value at the baseline visit.

### 11.2 Primary Efficacy Analysis and Sample Size Determination

An analysis of covariance (ANCOVA) model will be used to compare change from pre-treatment in Hb between the 3 vadadustat dosing groups and the placebo group. The model will include treatment assignment (3 dosed groups and 1 placebo group) and pre-treatment Hb value as a covariate. A step-down procedure will be used to control the overall type I error rate for the multiple comparisons. Testing of the highest dose compared with placebo will be conducted first. If and only if this comparison is significant, then testing will proceed to comparison of the next lower dose and placebo, and so on. Therefore, no multiplicity adjustment will be needed for this analysis.

The target enrollment will be approximately 48 subjects for the study with 12 subjects enrolled in each of the 4 treatment groups.

The study is powered based on a comparison of the highest dose vadadustat group (600 mg daily) and the placebo group. Based on the results from Study AKB-6548-CI-0005 that was conducted in the United States and evaluated vadadustat in patients with anemia secondary to

NDD-CKD, it is assumed that the expected mean Hb changes from baseline to Week 6 will be approximately 0 mg/dL for the placebo group and 1.35 g/dL for the highest dose vadadustat group (600 mg daily), with a common standard deviation of 0.68 g/dL across treatment groups. With these assumptions, the study with n=12 subjects per group will have >95% power to detect the difference between treatment group and control group, at 2-sided alpha of 0.05.

### **11.3 Preliminary (6-Week) Analysis**

In addition to the final analysis which will take place when all subjects have completed the study and will include all data collected, the 6-week efficacy and safety data will be summarized for administrative planning purposes after the last patient completes the primary efficacy period (Week 6). The preliminary analysis will be performed and interpreted by the sponsor and CRO study team personnel. Subjects and sites will not be unblinded to treatment allocation.

Individuals from the sponsor and CRO study teams who are unblinded for the development and reporting of preliminary analysis will not be involved in the conduct of the study after the preliminary analysis. As the study conduct and final analysis will not be modified by this analysis, no alpha adjustment is proposed. It is expected that this 6-week data will be identical for the preliminary administrative analysis and the final analysis of the complete dataset. Any changes between the preliminary analysis and the final analysis will be documented.

### **11.4 Study Populations**

#### **11.4.1 Analysis Population for the Safety Analyses**

The safety population is defined as all enrolled subjects who receive at least 1 dose of study medication. The safety population will be based on the actual treatment that patients received. All safety analyses will be performed using the safety population.

#### **11.4.2 Analysis Populations for the Efficacy Analyses**

The modified intent-to-treat (MITT) population is defined as all randomized subjects who receive at least 1 dose of study medication, have a pre-treatment Hb average defined as the average of the qualifying screening value and the baseline value, and at least one post-baseline Hb measurement. The MITT population will be based on the treatment to which patients are randomized.

The per-protocol (PP) population will consist of the subjects in the MITT population who have completed the study and have efficacy data through Week 6, have a study medication compliance of  $\geq 80\%$ , and do not have any major protocol deviations expected to significantly affect the primary efficacy endpoint. Subjects with major protocol deviations expected to significantly affect the primary efficacy endpoint will be identified and documented prior to data unblinding.

As sensitivity analyses, efficacy endpoints will also be analyzed using the PP population.

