## **7.6 Subject Completion and Individual Subject Discontinuation**

### **7.6.1 Subject Completion**

A subject will be considered as having completed the study after completing participation in the Week 18 visit (end of the 2-week follow-up period).

Note: Subjects who discontinue prematurely from the study or permanently discontinue study medication will complete the end-of-treatment (Week 16) visit followed in two weeks by the Week 18 visit (see Section 7.6.3).

See [Section 10.3.6](#) for information regarding follow-up of unresolved events.

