**Figure 5: Randomization Scheme of Study Treatment**

### 8.2.3 Blinding During the Study and Breaking the Blind

Throughout the study, all subjects, investigators, site personnel, and site pharmacists will be blinded to subject randomization status. All sponsor and CRO personnel will be blinded to randomization until the last subject completes the primary efficacy period (Week 6). At that time, the preliminary analysis will be performed and interpreted by sponsor and CRO study team personnel. Individuals from the sponsor and CRO study teams who are unblinded for the development and reporting of the preliminary analysis will not be involved in the conduct or interpretation of the study after the preliminary analysis. These activities will be transitioned to sponsor and CRO personnel who will remain blinded to randomization status throughout the remainder of the study.

The blind may be broken for individual subjects in the case of a medical emergency (where knowledge of the study drug administered would affect the treatment of the emergency). The decision to break the blind will be made on a case-by-case basis, at the discretion of the site investigator in collaboration with the sponsor's medical monitor/medical director (or designee).

The sponsor's and/or the CRO's safety medical monitor/medical director (or designee) and related safety personnel will be unblinded for safety data that would require assessment for expedited reporting.

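### The per-protocol set used for the Week 6 endpoint is defined by study completion at Week 18, so a Week 6 sensitivity analysis can turn on events after the placebo switch

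*Protocol*

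**What the plan says.** The protocol file holds more than one version. Section numbers here refer to the version whose section 11.2 specifies the ANCOVA.

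- Section 11.4.2 restricts the per-protocol (PP) population to "subjects in the MITT population who have completed the study and have efficacy data through Week 6", with at least 80% compliance and no major deviation expected to affect the primary endpoint. Subjects with such deviations "will be identified and documented prior to data unblinding". This one PP set serves as the sensitivity population for the efficacy endpoints.
- Section 7.6.1 defines the term used there: "A subject will be considered as having completed the study after completing participation in the Week 18 visit". It also sends subjects who stop early to an end-of-treatment visit and, two weeks later, to a Week 18 visit. Section 7.6.3 repeats this.
- Section 11.1 places the primary endpoint at Week 6.
- Sections 8.2.3 and 11.3 keep sponsor and CRO staff blinded until the last subject completes Week 6. The preliminary analysis is then run. Of its data, section 11.3 says: "It is expected that this 6-week data will be identical for the preliminary administrative analysis and the final analysis of the complete dataset".
- Section 8.2.5 switches placebo subjects to vadadustat at Week 6. Under section 8.2.6, a subject given rescue therapy stops study drug and is discontinued from the study.
- Section 11.6 tabulates discontinued subjects and completers as separate categories.

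**The concern.** A PP analysis of a Week 6 endpoint should ask whether the result holds among subjects who took the assigned treatment as planned up to Week 6. As written, membership also depends on staying in the study for a further 12 weeks. During those weeks the randomised comparison no longer exists: placebo subjects take vadadustat and all doses are titrated. A placebo subject with a valid Week 6 Hb could be dropped because of what happened later on active drug. Such exclusions say nothing about adherence before Week 6, and they may be related to Hb response.

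There is also a timing problem. Section 11.4.2 intends PP deviations to be settled under blind, but the completion criterion is still open for recent enrollees when the Week 6 data are first unblinded. And because early leavers also have a Week 18 visit, two programmers could build different PP sets from the same text.

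**Working it through.** **1. The plan's own figure.** Inputs from section 11.2: difference 1.35 g/dL, SD 0.68 g/dL, 12 per group, two-sided alpha 0.05.

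- Noncentrality = 1.35 / (0.68 × √(1/12 + 1/12)) = 1.35 / 0.2776 = 4.86.
- Noncentral t with 22 df: power 99.6%. With the 43 error df of a four-group ANCOVA with one covariate: 99.7%. Normal approximation: 99.8%.

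The stated figure of more than 95% is confirmed.

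**2. Timing.** Appendix A puts Week 6 at Day 43 and Week 18 at Day 127. The nominal gap is 127 − 43 = 84 days, or 12 weeks. That is how long after the Week 6 unblinding the last subject's completion status stays open, if that subject remains in the study.

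**3. One subject under three readings.** Take a compliant placebo subject with a Week 6 Hb value, switched at Week 6, given rescue at Week 12.

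| Reading of study completion | In the PP set? | Settled when |
|---|---|---|
| Week 18 on the study calendar; discontinued subjects are not completers (as section 11.6 separates them) | No | Week 12 |
| Any attended visit labelled Week 18 counts (sections 7.6.1 and 7.6.3) | Yes if the follow-up visit is attended, no if it is missed | About Week 14 |
| The words about Week 6 qualify both conditions | Yes | Week 6 |

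Under the first two readings, membership for a Week 6 comparison is decided by events after Week 6. Only the third avoids this, and it has to set aside the definition in section 7.6.1.

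**4. Size.** The protocol gives no dropout rate, so the loss between Week 6 and Week 18 is an assumption. Kept = 48 × (1 − loss), spread equally over four arms, with the same difference and SD:

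| Assumed loss | Subjects kept | Per arm | Power, 600 mg versus placebo |
|---|---|---|---|
| 0% | 48 | 12 | 99.6% |
| 10% | 43.2 | 10.8 | 99.2% |
| 20% | 38.4 | 9.6 | 98.4% |
| 30% | 33.6 | 8.4 | 96.7% |

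Precision is hardly touched. What matters is who leaves. If k of 12 subjects are removed and their mean change lies d below the arm mean, that arm's mean rises by k × d / (12 − k). With d set, for illustration, at one SD (0.68 g/dL), the shift is 0.68/11 = 0.06 g/dL for one subject and 1.36/10 = 0.14 g/dL for two. An equal shift in both arms cancels. Since the arms differ in what they received before Week 6, equality cannot be assumed, and the direction of any net bias cannot be predicted.

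**The case against.** Much of the case on the other side is sound.

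- **The PP set is only a sensitivity population.** True. The MITT analysis does not use the completion criterion.
- **The wording may be loose rather than deliberate.** The reference to Week 6 may have been meant to cover both conditions. But study completion is defined in section 7.6.1, so the text needs correcting whatever was meant.
- **Rescued subjects may count as completers.** They are referred to section 7.6.3, which asks them to attend the Week 18 assessments. On that reading only those who miss the follow-up visit are lost. This stands as an ambiguity: exclusion of valid data is possible under the text but not certain.
- **Completion matters for the Week 16 endpoints.** Also true, and a reason for two definitions rather than one.

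A reader might go further in four directions that the protocol does not support.

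- *That the PP set cannot be formed, or that section 11.3 is breached.* Section 11.3 requires no PP output at the administrative look. It expects the 6-week data to agree, without mentioning PP membership, and it provides for documenting changes. At the final analysis membership is known.
- *That unblinded staff would choose the set.* Section 8.2.3 removes unblinded individuals from later conduct and interpretation and hands over to blinded personnel. Visit attendance is a recorded fact, and the judgement on deviations is already to be made before unblinding.
- *That power for the lower doses suffers.* Expected changes of 0.5 and 0.7 g/dL appear only in superseded text built on linear regression. The current section 11.2 powers 600 mg versus placebo alone.
- *That the 80% compliance rule ejects strong responders whose drug was interrupted for high Hb.* Section 11.4.2 does not say that such interruptions count as non-compliance, and the calculation is the kind of detail a SAP commonly holds.

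**Conclusion.** The definition is wrong as written, with consequences limited to the sensitivity analysis. Sections 11.4.2 and 7.6.1 together make PP membership for a Week 6 endpoint depend on Weeks 7 to 18, after placebo subjects have switched. The last subject's status is known only 84 days after the Week 6 unblinding. Section 7.6.1 also leaves open whether an early discontinuer is a completer. The selection problem remains at the final analysis, so neither the administrative nature of the Week 6 look nor the handover to blinded staff removes it.

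The MITT primary analysis and the stated power are unaffected: power is 99.6% at 12 per arm and 96.7% even under an assumed 30% loss. The number of subjects concerned is unknown, and the loss rates and shifts shown above are illustrations. The completion criterion is fixed in the protocol itself, so this is not simply a detail left to the SAP. The defect gives no ground for renaming the Week 6 look as the primary analysis.

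**What to change.** - In section 11.4.2, for the Week 6 endpoints, replace the completion condition with: *have completed the primary efficacy period and have a Week 6 Hb value*.
- State that compliance for this set is assessed over Day 1 to Week 6.
- Fix PP membership for Week 6 before the Week 6 unblinding, in the same blinded review that section 11.4.2 already requires for deviations.
- If a completer set is wanted for the Week 16 endpoints, define it separately, and say there whether a subject who stopped early and attended the follow-up visit belongs to it.

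The cost is one replaced phrase and two or three added sentences, plus a check of Week 6 attendance and compliance in the blinded review before a look that is already planned. Nothing changes for subjects, visits or treatment.

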#### **5.2 Secondary Objectives and Endpoints**

The secondary objectives of this study are:

- To assess the safety, tolerability, pharmacokinetics (PK), and pharmacodynamics (PD) of oral vadadustat once daily dosing in Japanese subjects with anemia secondary to NDD-CKD during the 6-week, primary efficacy period
- To evaluate the effect of dose adjustments and demonstrate the maintenance effect on Hb during a 10-week dose adjustment and maintenance period

- To assess the time to reach the target Hb range from baseline

The efficacy endpoints that will be used to assess these objectives include the following:

- Time to reach target Hb level of 10.0-12.0 g/dL from baseline
- Mean Hb levels at the end of the primary efficacy period (Week 6) and at the end of the dose adjustment and maintenance period (Week 16)
- Proportion of subjects who achieve target Hb 10-12 g/dL at the end of the dose adjustment and maintenance period (Week 16)
- Mean change in Hb between pre-treatment and the end of the dose adjustment and maintenance period (Week 16)
- Mean change in hematocrit, RBC count, and reticulocyte count from baseline to the end of the primary efficacy period (Week 6) and the end of the dose adjustment and maintenance period (Week 16)
- Mean change in iron indices (ie, iron, total iron-binding capacity [TIBC], TSAT, and ferritin) and hepcidin from baseline to the end of the primary efficacy period (Week 6) and the end of the dose adjustment and maintenance period (Week 16)
- Proportion of subjects requiring rescue with RBC transfusion from baseline to the end of the primary efficacy period (Week 6) and the end of the dose adjustment and maintenance period (Week 16)
- Proportion of subjects requiring rescue with ESAs from baseline to the end of the primary efficacy period (Week 6) and the end of the dose adjustment and maintenance period (Week 16)
- Number of dose adjustments from baseline to the end of the dose adjustment and maintenance period (Week 16)
- Maintenance of iron sufficiency (defined as ferritin  $\geq$ 50 ng/mL and TSAT  $\geq$ 20%) from baseline to the end of the primary efficacy period (Week 6) and the end of the dose adjustment and maintenance period (Week 16)
- Plasma concentration profile of vadadustat and its metabolites using pre-dose sample from Week 4

The safety endpoints that will be used to assess these objectives include the following:

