## 8.2.6 Rescue Therapy Guidelines

- **ESA Rescue Therapy**

To standardize the use of ESA rescue therapy in the study, the following guidelines should be followed. ESA rescue therapy may be considered if:

- ESA is considered warranted by the investigator's judgment, AND
- The subject experiences a clinically significant worsening of anemia or symptoms of anemia, AND
- The subject has a confirmed Hb level <9.0 g/dL as defined by two consecutive Hb levels <9.0 g/dL. The investigator may schedule the subject to return for an unscheduled visit to confirm Hb level <9.0 g/dL prior to the subsequent scheduled study visit.

If clinically indicated, the investigator at his/her discretion may initiate ESA rescue therapy without a confirmatory Hb level <9.0 g/dL if the first 2 criteria listed above are met.

- **RBC Transfusion**

Investigators should use their local institution's transfusion guidelines when determining whether to transfuse a study subject.

Subjects who initiate rescue therapy (either ESA rescue therapy or RBC transfusion) will be required to stop study drug treatment and will be discontinued from the study (see [Section 7.6.3](#)).

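### The per-protocol repeat of the two rescue endpoints to Week 6 is forced to about 0% in every arm, because rescue itself generally removes a subject from that set

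*Protocol*

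**What the plan says.** Section numbers refer to the protocol version whose primary analysis is the ANCOVA with step-down testing.

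- Section 5.2 opens its list with "The efficacy endpoints that will be used to assess these objectives include the following". The list contains "Proportion of subjects requiring rescue with RBC transfusion from baseline to the end of the primary efficacy period (Week 6") and "Proportion of subjects requiring rescue with ESAs from baseline to the end of the primary efficacy period (Week 6"), each also taken to Week 16.
- Section 8.2.6 says that subjects who start either form of rescue "will be required to stop study drug treatment and will be discontinued from the study".
- Section 11.4.2 defines PP as "subjects in the MITT population who have completed the study and have efficacy data through Week 6", with at least 80% compliance and no major deviation expected to affect the primary endpoint.
- The same section requires, for the modified intent-to-treat (MITT) set, one dose, a pre-treatment Hb average "and at least one post-baseline Hb measurement".
- Section 11.4.2 then closes with "As sensitivity analyses, efficacy endpoints will also be analyzed using the PP population". It makes no exception for rescue.

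**The concern.** A sensitivity analysis is useful only if it could come out differently from the main analysis for reasons that bear on the treatment. Here, membership of the analysis set depends on the outcome being counted. Rescue leads to discontinuation, discontinuation generally means no Week 6 efficacy data, and PP requires those data. The PP rescue proportion to Week 6 is then close to zero in every arm, including placebo, and any real difference between arms disappears from that table. A reader who meets it under a sensitivity label could take it as support for a low rescue rate, when it shows only how the set was chosen.

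A smaller form of the same question arises for MITT. It requires a post-baseline Hb, and the first scheduled one is at Week 2. A subject rescued before then with no later Hb would leave both numerator and denominator.

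**Working it through.** **Step 1: the plan's own figures.** The protocol states no expected rescue rate and no power for rescue. Its one power figure is for Hb (section 11.2): difference 1.35 g/dL, SD 0.68 g/dL, 12 per group, two-sided alpha 0.05, power above 95%. The standard error is 0.68 × √(2/12) = 0.278 and the noncentrality is 1.35/0.278 = 4.86. Power is 99.6% with a two-sample t (22 df), 99.7% with four-group ANCOVA (43 df) and 99.8% by the normal approximation. The stated figure is confirmed, and the rescue point does not touch it.

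**Step 2: the set logic to Week 6.**

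1. Rescue before the Week 6 visit means drug is stopped and the subject is discontinued (8.2.6).
2. Such a subject has an end-of-treatment visit, within a day of stopping if possible, and a follow-up visit two weeks later (7.6.3, 9.4.8). The regular Week 6 visit is not part of that path.
3. PP needs efficacy data through Week 6 (11.4.2), which the subject therefore generally lacks.
4. So the PP numerator for rescue to Week 6 is generally zero. This step rests on the data clause alone and does not depend on how completion is read.

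**Step 3: size.** The rescue counts below are assumptions. The PP column supposes that all non-rescued subjects qualify; other exclusions would shrink its denominator and leave the zero.

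| Rescued by Week 6, of 12 dosed | All dosed | PP |
|---|---|---|
| 1 | 1/12 = 8.3% | 0/11 = 0% |
| 2 | 2/12 = 16.7% | 0/10 = 0% |
| 3 | 3/12 = 25.0% | 0/9 = 0% |
| 4 | 4/12 = 33.3% | 0/8 = 0% |

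For the second row, the exact 95% interval is 2.1% to 48.4% among all dosed, and the PP upper limit is 30.8%.

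**Step 4: where the zero can fail.**

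- A rescue inside the Week 6 window (Day 43 ± 3) with an Hb drawn leaves Week 6 data.
- A rescue near Day 29 has its follow-up CBC at about Day 29 + 14 = Day 43. If that post-rescue Hb is counted as Week 6, the data clause is met. The 80% compliance rule might still exclude the subject: 28 days of dosing out of 42 planned is 66.7%. That takes planned days as the denominator, which the protocol does not specify.

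**Step 5: rescues in Weeks 7 to 16.** These subjects can have Week 6 data, so the completion clause decides. Section 7.6.1 defines completion by the Week 18 visit and also sends discontinued subjects to that visit, which would let a rescued subject count as a completer. Section 11.6 lists discontinued and completing subjects as separate dispositions, which would not. The text does not settle it.

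**Step 6: MITT.** Loss requires a rescue before Week 2 and no Hb at end of treatment or follow-up. One such subject in an arm of 12 changes 1/12 = 8.3% to 0/11 = 0%; with two rescued and one lost, 2/12 = 16.7% becomes 1/11 = 9.1%.

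**The case against.** The strongest reply has four parts.

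**Detail belongs to the SAP.** Section 11 leaves the secondary analyses to that plan, which is not at hand. This is fair for anything the protocol leaves open. Here 11.4.2 itself fixes both the membership rule and its use for efficacy endpoints, so a SAP that follows it inherits the problem and one that avoids it departs from the protocol.

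**Exclusion is not absolute.** A reader might infer that no rescued subject can ever be in PP, or that the PP rate is exactly zero by construction at both time points. The documents do not support that. Sections 7.6.1, 7.6.3 and 9.4.8 send discontinued subjects to the Week 18 visit, so a Week 7 to 16 rescue may remain in PP, and the Week 6 window leaves a narrow gap as well. This part of the reply stands.

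**Rescues would be visible elsewhere.** Section 7.6.2 makes rescue for worsening anemia a recorded reason for stopping drug, section 11.6 tabulates discontinuations with reasons, and section 9.3.1 has rescue reviewed from the first post-baseline visit onward. This stands too: the PP table would mislead on its own, but it would not hide the events from the report.

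**The MITT loss is remote.** Any one post-baseline Hb suffices, the confirmed ESA criterion itself rests on Hb values, and CBCs are requested at end of treatment and follow-up. A reader might infer that the main analysis materially drops early failures; the text supports only a rare possibility.

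**Conclusion.** The concern holds for the PP repeat of the ESA-rescue and RBC-transfusion proportions to Week 6. That analysis selects on its own outcome and will return about 0% in every arm, against 8.3% to 33.3% among dosed subjects if 1 to 4 of 12 are rescued. Those counts are assumed, since the protocol gives none. The conclusion rests on rescued subjects being discontinued as section 8.2.6 requires and on no post-rescue Hb being counted as the Week 6 value.

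To Week 16 the result is undetermined until completion is given one meaning. The MITT point is minor. The consequence is confined to sensitivity tables for two secondary endpoints. It is worth correcting because the protocol itself prescribes those tables and the correction is nearly free.

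**What to change.** Add one sentence to section 11.4.2 and carry it into the SAP: the ESA-rescue and RBC-transfusion proportions, to Week 6 and to Week 16, are analysed in all randomised subjects who took at least one dose, by randomised arm, and are not repeated in the PP set. Keep PP for the Hb and pharmacodynamic endpoints.

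This removes the Week 6 problem, makes the reading of completion irrelevant for these two endpoints, and closes the small MITT gap. It costs one sentence in each document. Section 9.3.1 already has rescue reviewed at the visits after Day 1, so no further data, visits or subjects are needed, and no rule for giving rescue changes.
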